Appendix 14 Protocol Deviations

The investigator should not deviate from the protocol, except where necessary to eliminate an immediate hazard to trial subjects. Should other unexpected circumstances arise that will require deviation from protocol-specified procedures, the investigator should consult with the Responsible Medical Monitor (and Independent Ethics Committee [IEC], as required) to determine the appropriate course of action.

Protocol deviations due to COVID-19 illness and/or control measures should be documented with the reason for the deviation.

Appendix 15 Ethics and Regulations

Independent ethics committees and competent authorities

The clinical trial authorization granted by the competent authority (CA) and a favorable opinion from the relevant IEC(s) will be obtained prior to the start of the trial. The local authorities will be notified about the trial as required by law.

The CA and the IEC will be notified about the end of the trial and a report summarizing the trial results will be sent to the CA and the IEC within 1 year after the end of the trial. If the trial is terminated early, the CA and the IEC will be notified within 15 days.

Ethical conduct of the trial

The trial will be conducted in accordance with the ethical principles set forth in the Declaration of Helsinki (including amendments).

Subject information and consent

Written informed consent will be obtained from all subjects prior to entry into the trial. The investigator will explain to each subject orally and in writing (subject information sheet) the nature, significance, risks and implications of the trial before inclusion. In particular, the subjects will be informed about the following:

- The possibility of withdrawing from the clinical trial at any time by revoking the consent and without any resulting disadvantage.
- How personal and health-related data will be collected and used during the trial.

All subjects will receive a copy of the subject information sheet and a copy of their signed and dated informed consent form.

All subjects will be insured against injury caused by their participation in the trial according to legal requirements. They will be informed about the insurance and the resulting obligations on their part.

Legal and regulatory requirements

This trial will be carried out in accordance with GCP as required by European Union (EU) Directive 2001/20/EC and the relevant laws and regulations of the country in which the trial takes place.

Insurance policy

The sponsor will obtain liability insurance covering his and the investigator's responsibility as well as the responsibility of any person involved in the conduct of the trial, provided there is proper adherence to the protocol. An insurance certificate will be provided by the sponsor to the IEC, if required.

Appendix 16 Biological Samples and Record Retention

Biological Samples Retention and Destruction

Collected specimens (blood) will be processed, stored and frozen appropriately for analysis. The sponsor has put into place a system to protect subjects' personal information to ensure optimal confidentiality and defined standard processes for sample and data collection, storage, analysis, and destruction. Excess biological specimens may be further tested with regard to investigation of the vaccine effect.

Retention of trial records

Records and source documents pertaining to the conduct of the trial and the distribution of the investigational medicinal product (e.g., informed consent forms [ICFs], laboratory slips, vaccination inventory records, and other pertinent information) must be retained by the investigator for a period of at least 15 years.

1. INTRODUCTION

This document outlines the statistical methods to be implemented during the analyses of data collected within the scope of CureVac AG protocol CV-7202-104 [A non-randomized, open label, controlled, dose-escalation, phase I clinical trial to evaluate the safety, reactogenicity and immunogenicity of one or two administrations of candidate rabies mRNA vaccine CV7202 in healthy adult subjects]. The purpose of this plan is to provide specific guidelines from which the statistical analyses will proceed. Any deviations from this plan will be documented in the clinical trial report.

2. TRIAL DOCUMENTS

The following trial documents are used for the preparation of the statistical analysis plan:

- Protocol version 2.0, 30 April 2020
- Annotated electronic case report form (eCRF), Version 6.0, 28 November 2019
- Data management plan version 3.0, 14 June 2019
- Immunomonitoring analysis plan version 1.0, 14 January 2020

3. TRIAL OBJECTIVES

3.1 Primary Objective

The primary objective of the trial is to assess the safety and reactogenicity profile of CV7202 administered intramuscularly (i.m.) to healthy adults (18-40 years old), as a range of doses (1, 2 and 5 µg) in 1- or 2-dose regimens.

3.2 Secondary Objective

Secondary objectives include:

For safety

- To assess the safety profile of CV7202 administered i.m. to healthy adults (18-40 years old), as a range of doses (1, 2, and 5 µg) in 1- or 2-dose regimens in the period from 12 to 24 months after the last dose.

For the characterization of the humoral immune response

- To evaluate the potential protective immune responses to CV7202 and Rabipur® in healthy adults (18-40 years old), by assessing the percentages of subjects with Rabies Specific serum virus-neutralizing antibody titers (VNTs) ≥ 0.5 IU/ml.
- To evaluate the immunogenicity (VNTs) of CV7202 administered to healthy adults (18-40 years old), as a range of doses (1, 2, and 5 µg) in 1- or 2-dose regimens and the immunogenicity of Rabipur administered in a 3-dose regimen.

3.3 Exploratory Objectives

Exploratory objectives comprise:

For the evaluation of the innate immune response

- To evaluate the innate immune response to 1 or 2 doses of CV7202 compared with baseline.

For the evaluation of antigen specific T-cell response

- To evaluate the frequencies and functionalities of rabies virus glycoprotein (RABV-G)-specific T cells after 1 or 2 doses of CV7202 compared with baseline.

For the evaluation and characterization of the B-cell response

- To evaluate the frequencies of RABV-G-specific B cells after 1 or 2 doses of CV7202 compared with baseline.
- To evaluate the effect of vaccination on B-cell phenotype and activation after 1 or 2 doses of CV7202 compared with baseline.
- To evaluate the effect of vaccination on B-cell clonality after 1 or 2 doses of CV7202 compared with baseline.

For the characterization of the humoral immune response

- To evaluate RABV-G-specific antibody responses throughout the trial including the follow-up period by assessing immunoglobulin M (IgM), IgG, and IgA levels.
- To characterize the nature and quality of the RABV-G-specific antibody response, by measuring the serum affinity and avidity after 1 or 2 doses of CV7202 and the breadth of neutralization against heterologous lyssaviruses with variant epitopes.

4. TRIAL DESIGN AND PLAN

This is a non-randomized, open label, controlled, dose-escalation, phase I clinical trial to evaluate the safety, reactogenicity, and immunogenicity of 1 or 2 i.m. administrations of candidate rabies messenger ribonucleic acid (mRNA) vaccine CV7202 in healthy adult subjects.

Subjects will be enrolled in 2 trial sites, 1 in Germany, 1 in Belgium.

Approximately 52 subjects will be enrolled sequentially in up to 4 trial groups to receive either a dose of CV7202 containing different mRNA content or Rabipur. In a first CV7202 group, 10 subjects have received a dose containing 5 µg mRNA. A dose of 1 or 2 µg mRNA will be administered to 2 additional groups of 16 subjects each, of whom 8 in each group will be administered a second dose 28 days later. A control group of 10 subjects will receive 3 doses of the licensed vaccine Rabipur according to the manufacturer's recommendations. Safety and immunogenicity assessments will be made up to 2 years following the last dose administration.

Specified safety data will be reviewed by an internal safety review committee and a data safety monitoring board on a pre-defined schedule. At each planned safety review, safety data will be reviewed, and a GO/NO GO decision made accordingly for enrollment of further subjects and administration of subsequent doses.

Enrollment will be staggered in Groups 2 to 4 to ensure the safety of the participating subjects. Enrollment into Group 1 (1.0 ml Rabipur) will not be staggered, since the clinical safety of Rabipur is well established.

Subjects will be enrolled at pre-screening (Day -90 to -1) to receive either CV7202 starting on Day 1 as 1 dose or 2 doses (at least 28 days apart), or 3 doses of control vaccine (Rabipur). Follow-up for safety and immunogenicity is planned up to 24 months after the last dose; therefore, the expected duration of participation for each subject is approximately 24 months after the last dose.

Please refer to protocol section 5 for more details of trial design, protocol section 6 for trial population and protocol section 7 for discontinuation/withdrawal criteria.

5. DETERMINATION OF SAMPLE SIZE

No statistically based sample size estimation was performed.

6. GENERAL ANALYSIS CONSIDERATIONS

The statistical analyses will be reported using summary tables, listings, and figures (TLFs). The International Council for Harmonisation (ICH) numbering convention will be used for all TLFs. Due to the exploratory nature of this trial, only descriptive statistics will be used; therefore, no confirmatory statistical inference will be performed.

Continuous variables will be summarized with means, standard deviations, medians, minimums, maximums, and valid cases. Other summaries may be used as appropriate.

Categorical variables will be summarized by counts and by percentage of subjects in corresponding categories. Percentages for missing values are omitted and do not account for the percent calculation of other categories. Percentages are routinely based on the total category count excluding the missing category if not otherwise mentioned. Percentages showing a rate relative to the total number of subjects in this group are given in special tables (eg, adverse event [AE] tables). Footnotes will specify the percent basis in those cases.

All summary tables will be presented by vaccination group (in the tables denoted as 'dosage/vaccine'). Baseline summaries will also include a total summary column. The CV7202 dose groups will be reported from the lowest to the highest dose. Selected tables will also display by dose regimen (in the tables denoted as 'treatment group').

Individual subject data obtained from the eCRFs or data from external sources like immunogenicity laboratory data and any derived data will be presented by subject in data listings. All post-baseline unscheduled assessments will be listed only. Only scheduled post-baseline safety measurements will be summarized, if appropriate. Should a repeat occur at a scheduled visit then only the last result per visit will be considered for the summary tables.

The analyses described in this plan are considered a priori, in that they have been defined prior to database lock. Any analyses performed subsequent to finalization of this statistical analysis plan will be considered post hoc and exploratory. Post hoc analyses will be labeled as such on the output and identified in the clinical trial report.

All analyses and tabulations will be performed using SAS® software Version 9.4 or higher. Tables, listings, and figures will be presented in rich text format. The process for SAS program validation and quality control (QC) for programs and outputs is documented in the Synteract working instruction “SAS programming quality control”, and trial-specific QC requirements can be found in Appendix B: SAS Programming QC requirements.

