| | 3 | Significant; any use of narcotic pain reliever and/or prevents daily activity |
| Fatigue | 0 | Absent |
| | 1 | Mild, no interference with normal activity |
| | 2 | Moderate, some interference with normal activity |
| | 3 | Significant, prevents normal activity |
| Chills | 0 | Absent |
| | 1 | Mild, no interference with normal activity |
| | 2 | Moderate, some interference with normal activity |
| | 3 | Severe, prevents normal activity |
| Myalgia | 0 | Absent |
| | 1 | Mild, no interference with normal activity |
| | 2 | Moderate, some interference with normal activity |
| | 3 | Significant, prevents normal activity |
| Arthralgia | 0 | Absent |
| | 1 | Mild, no interference with normal activity |
| | 2 | Moderate, some interference with normal activity |
| | 3 | Significant, prevents normal activity |
| Nausea/ Vomiting | 0 | Absent |
| | 1 | Mild, no interference with activity and/or 1 – 2 episodes/ 24 hours |
| | 2 | Moderate, some interference with activity and/or >2 episodes/ 24 hours |
| | 3 | Severe, prevents daily activity, requires outpatient i.v. hydration |
| Diarrhea | 0 | Absent |
| | 1 | 2 – 3 loose stools or <400 g/24 hours |
| | 2 | 4 – 5 stools or 400 – 800 g/24 hours |
| | 3 | 6 or more watery stools or >800 g/24 hours or requires outpatient IV hydration |

*FDA toxicity grading scale [25]; i.v. = Intravenous.

Laboratory data will be graded according with the FDA toxicity grading scale [25] and the Common Terminology Criteria for Adverse Events (CTCAE) Version 5.0 [26]. These guidelines however are dependent upon institutional normal parameters. Institutional normal reference ranges should be provided to demonstrate that they are appropriate.

AEs with a suspected immune mediated disease etiology will be considered AESIs. The list of AESI is provided in (Appendix 10).

Definitions and Procedures for Recording, Evaluating, Follow-up, and Reporting of AEs are provided in Appendix 11.

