10.3.5 Safety Analyses

The following safety and reactogenicity data will be summarized descriptively: vital signs, and vaccination site reactogenicity assessment.

The occurrence of solicited local and systemic AEs reported on the day of each vaccination and the 7 subsequent days and unsolicited AEs reported on the day of each vaccination and the 28 subsequent days will be presented.

The safety measurements will include:

1. AEs (type, intensity, frequency and relationship to vaccination), i.e. incidence and severity of AEs for both solicited local and systemic events (occurring on the day of vaccination and the 7 subsequent days) and unsolicited events (occurring on the day of vaccination and the 28 subsequent days).
2. SAEs, MAAEs and AEs leading to trial or vaccine withdrawal up to 12 months post last dose. After Visit 15 (Month 12), only SAEs and MAAEs that according to the

investigator are considered to be related to study vaccination will be collected.

3. Intercurrent medical conditions and AESIs throughout the trial.
4. Local reactogenicity assessment of injection site in all subjects.

Further, the incidence of AEs will be summarized in frequency tables by Medical Dictionary for Regulatory Activities (MedDRA) terms (system organ class [SOC] and preferred term [PT]). AEs that are reported as related to the test vaccine will be considered trial vaccine-related; missing classifications concerning trial vaccine relationship will also be considered trial vaccine-related.

Concomitant medications and vaccinations will be coded and summarized. Physical examination data will be listed.

Clinical laboratory test results with values below/above the reference range will be counted.

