- Overall summary of unsolicited AEs that contain an overview of each item below
- All AEs
 - Mild (grade 1) AEs
 - Moderate (grade 2) AEs
 - Severe (grade 3) AEs
- Related AEs
 - Mild (grade 1) related AEs
 - Moderate (grade 2) related AEs
 - Severe (grade 3) related AEs
- SAEs
- Related SAEs
- MAAEs
- AEs leading to withdrawal from study
- AEs leading to discontinued vaccination

- AESIs

Laboratory data will be graded by the site in the AE form according to the United States Food and Drug Administration toxicity grading scale and the Common Terminology Criteria for Adverse Events Version 5.0.

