11.7 Safety Laboratory Evaluation

Laboratory parameters (hematology, biochemistry, and coagulation) will be summarized using descriptive statistics at baseline and at each postbaseline time point. The categorization into low-normal-high (below lower reference range/ within reference range/ above upper reference range) will also be summarized. In summary tables, results below or above the detection limit are set to the detection limit.

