14.3.7.3.1 Hematology, Safety Analysis Set

Parameter (unit)	CV7202 1 µg (N = xx)	CV7202 2 µg (N = xx)	CV7202 5 µg (N = xx)	Rabipur (N = xx)
Parameter (unit)	Visit xx			
n	xx	xx	xx	xx
Mean (SD)	xx.x (xx.xx)	xx.x (xx.xx)	xx.x (xx.xx)	xx.x (xx.xx)
Median	xx.x	xx.x	xx.x	xx.x
Min, Max	xx, xx	xx, xx	xx, xx	xx, xx
Low	xx (xx.x%)	xx (xx.x%)	xx (xx.x%)	xx (xx.x%)
Normal	xx (xx.x%)	xx (xx.x%)	xx (xx.x%)	xx (xx.x%)
High	xx (xx.x%)	xx (xx.x%)	xx (xx.x%)	xx (xx.x%)
Visit xx	...			

Values are categorized into low-normal-high (below lower reference range/ within reference range/ above upper reference range). In the occurrence of a repeat, only the last valid result is considered.

Unscheduled visits are not presented for this summary. Results reported as below or above the detection limit are set to the detection limit.

PROGRAM SOURCE: tlf-###, DATA CUT OFF DATE: DDMMYYYY

RUN DATE: DDMMYYYY hh:mm

Programming note:

Display for all hematology parameters and all visits and timepoints with data collected for these parameters.

Number of decimals will vary by parameter - in general present mean, median to 1 decimal more than individual data, SD to 2 decimals more than individual data. Refer to SAP.

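### Laboratory tables count only the last valid result per scheduled visit, so a valid out-of-range value with a normal same-visit repeat is counted as normal, and values found at unscheduled visits are never counted

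*SAP*

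**What the plan says.** **Repeats.** SAP section 6 sets the general rule: "Should a repeat occur at a scheduled visit then only the last result per visit will be considered for the summary tables". The footnote of shell 14.3.7.3.1 (hematology) words it slightly differently: "In the occurrence of a repeat, only the last valid result is considered". Shells 14.3.7.3.2 (biochemistry) and 14.3.7.3.3 (coagulation) repeat that table. The SAP does not define a valid result.

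**Unscheduled results.** SAP section 6 says "All post-baseline unscheduled assessments will be listed only" and "Only scheduled post-baseline safety measurements will be summarized, if appropriate". The hematology footnote says the same for its table.

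**What is tabulated.** SAP 11.7 plans descriptive statistics by time point and adds: "The categorization into low-normal-high (below lower reference range/ within reference range/ above upper reference range) will also be summarized". The table index has no other laboratory summary: no worst-value table, no any-time-post-baseline count and no shift table.

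**The protocol.** Protocol 10.3.5 says: "Clinical laboratory test results with values below/above the reference range will be counted". It makes no exception for repeated or unscheduled tests. SAP section 12, on changes to the protocol's analyses, mentions only the removal of the per-protocol sets.

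**Where individual values remain.** Listing 14.3.4 shows abnormal laboratory values for each subject. Listings 16.2.8.1 to 16.2.8.3 show the reference limits, a high/low flag and the investigator's judgement of clinical significance. Under Protocol Appendix 11, a laboratory abnormality judged clinically significant is an adverse event.

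**The concern.** A likely reason to repeat a test is that the first value was out of range. If the repeat is then normal and both belong to the same scheduled visit, the table keeps the repeat and shows the subject as normal. The first value may have been a true, short-lived change after vaccination, yet it appears in no laboratory count. The Min and Max rows of the same table are built from the same selected values and lose it too.

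The unscheduled rule has a different effect. Protocol Appendix 6 allows additional tests at any time, and Protocol 5.1.2 allows extra safety blood sampling after a temporary halt. Unless such samples are set up as scheduled visits, an abnormality first seen in them is listed but never counted.

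Elsewhere the SAP keeps the highest grade: for solicited events over the diary days (11.2.1), for the investigator's injection-site assessment (11.2.3) and for unsolicited events by maximum intensity (shell 14.3.1.2.4). Laboratory data are treated the other way. SAP 6.1 also lets unscheduled values define baseline, although they do not count afterwards.

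Safety is the primary objective of this first-in-human trial, and the summary tables are where groups are compared. With 10 to 16 subjects per group, one subject more or less is visible.

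**Working it through.** The plan states no figure on this point, so there is nothing to reproduce. The check is of the rule itself, with simple arithmetic for size.

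**1. What each situation yields under the SAP**

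| Situation | Counted as | Effect |
|---|---|---|
| Valid out-of-range value, normal repeat, same scheduled visit | Normal | Out-of-range value leaves the counts |
| Valid out-of-range value, repeat in the same category, same visit | Low or high | None |
| Out-of-range value at a scheduled visit, normal re-test at an unscheduled visit | Low or high | None; the re-test is the one left out |
| Out-of-range value first found at an unscheduled visit | Not counted | Never enters the table |
| First result invalid, repeat normal | Normal | Appropriate |

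The first and fourth rows are the defect. They arise from two separate rules.

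**2. Direction.** Compare the last-result rule with counting a subject-visit as out of range if any valid result at that visit is out of range. If the last valid result is out of range, both rules count it. If only an earlier valid result is, the last-result rule misses it. So at any visit the last-result count of out-of-range subjects is at most equal to the any-result count. The difference goes one way only.

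**3. Size of one superseded value.** SAP 6.4 reports 16 subjects vaccinated at 1 µg, 16 at 2 µg, 10 at 5 µg and 11 with Rabipur. Assuming every subject has a result at the visit:

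- 5 µg: 1/10 = 10.0% becomes 0/10 = 0%.
- Rabipur: 1/11 = 9.1% becomes 0/11 = 0%.
- 1 µg or 2 µg: 1/16 = 6.25%, shown as 6.3%, becomes 0/16 = 0%.

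**4. Overall size.** Let a be the share of subjects with a valid out-of-range first value at a visit, r the share of these repeated at the same visit, and v the share of those repeats that are normal. The tabulated share is t = a(1 − r·v), so t/a = 1 − r·v. The documents give neither r nor v. With r = 0 the ratio is 1; with r = v = 1 it is 0. The documents do not narrow that interval, so I state no overall percentage.

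**5. A check on the remedy.** A row for any post-baseline abnormality will also collect chance findings. Protocol Table 9.3 has safety laboratory draws at 12 visits; without screening and Day 1, 10 are post-dose. Visit 9 applies only to subjects vaccinated on Day 29, so single-dose subjects have 9. Assuming a 5% chance of an out-of-range value per test and independence between visits, the share of subjects flagged per parameter would be 1 − 0.95^10 = 40% with 10 visits and 1 − 0.95^9 = 37% with 9. Both assumptions are mine. The row therefore needs a caveat and should supplement the by-visit counts.

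**The case against.** The strongest reply has four parts.

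*The values stay visible.* Section 6 restricts only the summary tables. Superseded and unscheduled results remain in the listings, with flags and the investigator's assessment, and clinically significant ones enter the adverse event tables. With 53 subjects a listing of abnormal values can be read. This stands, and it confines the defect to the summary counts. It does not remove it, because a listing gives no count by group.

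*No endpoint or stopping rule is affected.* The primary and secondary safety endpoints are based on adverse events, SAP 11.1 places laboratory data among further safety variables, the group stopping rules are based on adverse events, and the DSMB sees safety laboratory data during the trial. This also stands. The effect is on descriptive tables in the report.

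*The protocol is not contradicted.* Protocol 10.3.5 does not say which result represents a visit, and Protocol 10.3.1 leaves the definition of analysis variables to the SAP. That is fair: the SAP narrows the protocol statement and does not reverse it. A narrowing that omits valid out-of-range results should still be declared in SAP section 12.

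*Same-visit repeats may be rare, and some only replace bad samples.* The schedule plans one safety draw per laboratory visit, and nothing gives a repeat rate or the reasons for repeats. This stands against any claim about overall size. It does not justify the rule, since excluding invalid results does not require discarding valid ones.

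**Conclusion.** The point holds for the summary counts. In tables 14.3.7.3.1 to 14.3.7.3.3 a valid out-of-range value followed by a normal repeat at the same scheduled visit is counted as normal, and an out-of-range value first found at an unscheduled visit is not counted. Both narrow Protocol 10.3.5 without a declaration in SAP section 12. One superseded value changes 10.0%, 9.1% or 6.3% to 0, depending on the group, provided all subjects have a result at that visit.

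A reader might infer more, but the documents do not support it:

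- *That leaving out unscheduled results also hides the value that prompted a re-test.* An unscheduled re-test leaves the scheduled abnormal value in the counts.
- *That a known, large share of abnormalities is hidden.* No repeat rate or normalisation rate is given, and a normal repeat may correct a spurious first value.
- *That data are lost.* They are in listings 14.3.4 and 16.2.8.1 to 16.2.8.3.
- *That the SAP abandons the protocol's laboratory grading.* Protocol 9.1 says "Laboratory data will be graded according with the FDA toxicity grading scale" and SAP 11.2.2 says "Laboratory data will be graded by the site in the AE form". The protocol sentence stands in its adverse event section and does not say who grades, and Protocol 10.3.5 promises no table of grades. Grading by the site is a permissible reading and a separate matter.

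**What to change.** In SAP section 6, SAP 11.7 and shells 14.3.7.3.1 to 14.3.7.3.3:

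1. Classify each subject-visit as low, normal or high from all valid results at that visit, so that an out-of-range result is counted even when a repeat is normal. State how a visit with both a low and a high value is shown.
2. Add a row for subjects with any post-baseline low value and any post-baseline high value, including repeats and unscheduled tests. Footnote that subjects tested more often have more chances to be counted.
3. Keep one value per visit for means.
4. Exclude results documented as technically invalid, and use one wording in section 6 and the shell footnotes, which now differ on whether the last result must be valid. Define valid.

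If the present rule is kept, declare it in SAP section 12 as a limit on Protocol 10.3.5.

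The cost is SAP wording and modest programming on data already collected. Abnormality counts will be slightly less favourable, and some chance out-of-range values will be included, most visibly in the new row.
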